14.3.3 T1 Gd+ lesion count

T1 GD+ lesion counts by Visit and Period are defined in Section 9 “Definition of Study Periods” and “Data Handling of MRI data”.

To evaluate further the course of T1 GD+ lesion appearance over time, T1 Gd+ lesions will be further classified as follows for each Visit:

- T1 Gd+ lesion count > 0
 - Yes (T1 Gd+ lesion count > 0)
 - No (T1 Gd+ lesion count = 0)

Analogously for new T1 Gd+ lesion count.

Analysis (Analysis Set)	Derivation	Statistical Analysis Methods	Missing data handling
Tertiary endpoints: Change from the Baseline Period in T1 Gd+ lesion count to the six months post-Baseline Periods			
Tertiary (FAS)	Period 6.1 (Baseline-Month 6): $\Delta T1(p_{6.1})$	Mixed-effects linear model for repeated measures, same as in Tertiary Analysis for Change from Baseline in CUA lesion count (see Section 14.3.1)	Same as in Tertiary Analysis for Change from Baseline in CUA lesion count (see Section 14.3.1)
Tertiary (FAS by subgroup "High-relapse activity")	Period 6.2 (Month 6-12): $\Delta T1(p_{6.2})$		
Tertiary (FAS by subgroup "Previous treatment with DMDs")	Period 6.3 (Month 12-18): $\Delta T1(p_{6.3})$ Period 6.4 (Month 18-24): $\Delta T1(p_{6.4})$		
Tertiary endpoints: Ratio of the six months post-Baseline Periods versus the Baseline Period in T1 Gd+ lesion count			
Tertiary (FAS)	Period 6.1 (Baseline-Month 6): $\#T1(p_{6.1})/\#T1(p_0)$	Generalized model assuming a negative binomial, same as in Tertiary Analysis for Change from Baseline in CUA lesion count (see Section 14.3.1)	Same as in Tertiary Analysis for Change from Baseline in CUA lesion count (see Section 14.3.1)
Tertiary (FAS by subgroup "High-relapse activity")	Period 6.2 (Month 6-12): $\#T1(p_{6.2})/\#T1(p_0)$		
Tertiary (FAS by subgroup "Previous treatment with DMDs")	Period 6.3 (Month 12-18): $\#T1(p_{6.3})/\#T1(p_0)$ Period 6.4 (Month 18-24): $\#T1(p_{6.4})/\#T1(p_0)$		
Tertiary endpoints: Change from the Baseline Period in T1 Gd+ lesion count to the yearly post-Baseline Periods			
Tertiary (FAS)	Period 12.1 (Baseline-Month 12): $\Delta T1(p_{12.1})$	Mixed-effects linear model for repeated measures as specified above.	Same as above for the mixed effect linear model with repeated measures.
Tertiary (FAS by subgroup "High-relapse activity")	Period 12.2 (Month 12-24): $\Delta T1(p_{12.2})$		
Tertiary (FAS by subgroup "Previous treatment with DMDs")			
Tertiary endpoints: Ratio of the yearly post-Baseline Periods versus the Baseline Period in T1 Gd+ lesion count			
Tertiary (FAS)	Period 12.1 (Baseline-Month 12): $\#T1(p_{12.1})/\#T1(p_0)$	Generalized model as specified as above.	Same as above for the generalized model.
Tertiary (FAS by subgroup "High-relapse activity")	Period 12.2 (Month 12-24): $\#T1(p_{12.2})/\#T1(p_0)$		
Tertiary (FAS by subgroup "Previous treatment with DMDs")			

Analysis (Analysis Set)	Derivation	Statistical Analysis Methods	Missing data handling
Tertiary endpoint: Change from the Baseline Period in T1 Gd+ lesion count to the 2-year post-Baseline Period			
Tertiary (FAS)	Period 24.1 (Baseline-Month 24): $\Delta T1(p_{24.1})$	Mixed-effects linear model same as in Tertiary Analysis for Change from Baseline in CUA lesion count (see Section 14.3.1)	Same as in Tertiary Analysis for Change from Baseline in CUA lesion count (see Section 14.3.1)
Tertiary (FAS by subgroup "High-relapse activity")			
Tertiary (FAS by subgroup "Previous treatment with DMDs")			
Tertiary endpoints: Ratio of the 2-year post-Baseline Period versus the Baseline Period in T1 Gd+ lesion count			
Tertiary (FAS)	Period 24.1 (Baseline-Month 24): $\#T1(p_{24.1}) / \#T1(p_0)$	Generalized model assuming a negative binomial distribution with the following adjusting factors: 
 • Age (years), • EDSS at Baseline ($\leq 3, >3$), Estimated T1 Gd+ lesions count for the Periods as well as the ratios of the post-Baseline Period versus the Baseline Period, and corresponding Standard Errors (SE) will be presented including estimated fixed effects including the SE, 2-sided p-values and 95% CI.	Same as above for the generalized model.
Tertiary (FAS by subgroup "High-relapse activity")			
Tertiary (FAS by subgroup "Previous treatment with DMDs")			
Tertiary endpoint: Change from Baseline in T1 Gd+ lesion count by Visit			
Tertiary (FAS)	Change from Baseline in T1 Gd+ lesion count at Month i Visit, where $i = 1, 2, 3, 6, 12, 15, 18$ and 24.	Mixed-effects linear model for repeated measures, same as in Tertiary Analysis for Change from Baseline in CUA lesion count (see Section 14.3.1)	Same as in Tertiary Analysis for Change from Baseline in CUA lesion count (see Section 14.3.1)
Tertiary (FAS by subgroup "High-relapse activity")			
Tertiary (FAS by subgroup "Previous treatment with DMDs")			
Tertiary Endpoint: T1 Gd+ lesion count > 0			
Tertiary (FAS)	Cross-tabulation for each post-Baseline Period 
 • No: $\#T1(p_{\text{post-Baseline}}) = 0$ • Yes: $\#T1(p_{\text{post-Baseline}}) > 0$ vs Baseline Period: 
 • No: $\#T1(p_0) = 0$ • Yes: $\#T1(p_0) > 0$ 	McNemar Test.	Same as for McNemar test in Section 14.3.1
Tertiary (FAS by subgroup "High-relapse activity")			
Tertiary (FAS by subgroup "Previous treatment with DMDs")			

Analysis (Analysis Set)	Derivation	Statistical Analysis Methods	Missing data handling
Tertiary endpoint: New T1 Gd+ lesion count			
Tertiary (FAS)	New T1 Gd+ lesion count at Baseline and at the Month i Visit, where i= 1, 2, 3, 6, 12, 15, 18 and 24, as well as at selected post-Baseline Periods, i.e. p12.1, p12.2, p24.	Descriptive summary statistics.	
Tertiary (FAS by subgroup "High-relapse activity")			
Tertiary (FAS by subgroup "Previous treatment with DMDs")			
Tertiary endpoint: New T1 Gd+ lesion count > 0			
Tertiary (FAS)	Cross-tabulation for each post-Baseline Period 
 No: # T1 ($p_{\text{post-Baseline}}=0$) Yes: # T1 ($p_{\text{post-Baseline}}>0$) vs Baseline Period: 
 No: # T1 ($p_0=0$) Yes: # T1 ($p_0>0$) 	Frequency table with percentages.	
Tertiary (FAS by subgroup "High-relapse activity")			
Tertiary (FAS by subgroup "Previous treatment with DMDs")			
Tertiary endpoint: Change from Baseline in Mean T1 Gd+ lesion count^(a)			
Tertiary (FAS)	Period 1 (Month 1-6): $\Delta T1(p_1)$	Same as in the Primary Analysis (see Section 14.1.1)	Same as in the Primary Analysis (see Section 14.1.1)
	Period 2 (Month 2-6): $\Delta T1(p_2)$		
	Period 3 (Month 3-6): $\Delta T1(p_3)$		
$\Delta T1(p_i)$ = Difference in Mean T1 Gd+ lesion count between Period i and the Baseline Period $\$$ =Sequential Visit Periods (a) 6-month interim analysis			

Repeated mixed-effects linear model

As defined in Section 14.3.1 applying adaptations to the endpoints, factors and covariates listed in the table above.

Generalized linear model assuming negative binomial distribution:

As defined in Section 14.3.1 applying adaptations to the endpoints, factors and covariates listed in the table above.

14.3.4 T1 Gd+ lesion volume

Analysis (Analysis Set)	Derivation	Statistical Analysis Methods	Missing data handling
Tertiary endpoint: Change from Baseline in the T1 Gd+ lesion volume			
Tertiary (FAS)	The absolute volume and change from Baseline to Month i Visit, where i= 1, 2, 3, 6, 12, 15, 18 and 24, in T1 Gd+ lesion volume by Visit	Descriptive summary statistics.	

14.3.5 T1 hypointense lesion count

Analysis (Analysis Set)	Derivation	Statistical Analysis Methods	Missing data handling
Tertiary endpoint: Change from Baseline in the T1 hypointense lesion count			
Tertiary (FAS)	The absolute count and change from Baseline to Month i Visit, where i= 1, 2, 3, 6, 12, 15, 18 and 24, in T1 hypointense lesion count by Visit	Descriptive summary statistics.	

14.3.6 T1 hypointense lesion volume

Analysis (Analysis Set)	Derivation	Statistical Analysis Methods	Missing data handling
Tertiary endpoint: Change from Baseline in the T1 hypointense lesion volume			
Tertiary (FAS)	The absolute volume and change from Baseline to Month i Visit, where i= 1, 2, 3, 6, 12, 15, 18 and 24, in T1 hypointense lesion volume by Visit	Descriptive summary statistics.	

14.3.7 Active T2 lesion count

The number and changes from Baseline of the different types of active T2 lesions will be presented by Period or Visit.

Active T2 lesion count will be further classified as follows for each Visit:

- Active T2 lesion count > 0
 - Yes (Active T2 lesion count > 0)
 - No (Active T2 lesion count = 0)

Analysis (Analysis Set)	Derivation	Statistical Analysis Methods	Missing data handling
Tertiary endpoint: Changes in the standardized total active T2 lesion count (without T1 Gd+) during pre-defined post-Baseline Periods compared to the Baseline Period^(a)			
Tertiary (FAS)	Change from Baseline of the standardized total active T2 lesion count without T1 Gd+ to Periods 1-3.	Descriptive summary statistics.	
Tertiary endpoint: Changes in standardized total active T2 lesion count during pre-defined post-Baseline Periods compared to the Baseline Period (i.e., the Period from Screening to Baseline)^(a)			
Tertiary (FAS)	Period 3 (Month 3-6): $\Delta T2(p3)$	Same as in the Primary Analysis (see Section 14.1.1)	Same as in the Primary Analysis (see Section 14.1.1)
Tertiary (FAS by subgroup "High-relapse activity")			
Tertiary (FAS by subgroup "Previous treatment with DMDs")	Period 2 (Month 2-6): $\Delta T2(p2)$		
Tertiary (FAS for subset "Baseline Period CUA count > 0")	Period 1 (Month 1-6): $\Delta T2(p1)$		
Tertiary endpoint: Total active T2 Lesion count by Visit^(a)			
Tertiary (FAS)	Change from Baseline in total active T2 Lesion count at Month i Visit, where i=2, 3, 6.	Same as in the Tertiary Analysis of Change from Baseline in T1 Gd+ lesion count (see Section 14.3.3)	Same as in the Tertiary Analysis of Change from Baseline in T1 Gd+ lesion count (see Section 14.3.3)
Tertiary (FAS by subgroup "High-relapse activity")			
Tertiary (FAS by subgroup "Previous treatment with DMDs")			
Tertiary (FAS for subset "Baseline Period CUA count > 0")			
Tertiary endpoints: Change from the Baseline Period in Annualized Active T2 lesion count to the six months post-Baseline Periods			
Tertiary (FAS)	Period 6.1 (Baseline-Month 6): $\Delta T2(p_{6.1})$	Mixed-effects linear model for repeated measures, same as in Tertiary Analysis for Change from Baseline in CUA lesion count (see Section 14.3.1)	Same as in Tertiary Analysis for Change from Baseline in CUA lesion count (see Section 14.3.1)
Tertiary (FAS by subgroup "High-relapse activity")	Period 6.2 (Month 6-12): $\Delta T2(p_{6.2})$		
Tertiary (FAS by subgroup "Previous treatment with DMDs")	Period 6.3 (Month 12-18): $\Delta T2(p_{6.3})$ Period 6.4 (Month 18-24): $\Delta T2(p_{6.4})$		

Analysis (Analysis Set)	Derivation	Statistical Analysis Methods	Missing data handling
Tertiary endpoints: Ratio of the six months post-Baseline Periods versus the Baseline Period in Annualized Active T2 lesion count			
Tertiary (FAS)	Period 6.1 (Baseline-Month 6): #T2(p _{6.1})/#T2(p ₀)	Generalized model assuming a negative binomial, same as in Tertiary Analysis for Change from Baseline in CUA lesion count (see Section 14.3.1)	Same as in Tertiary Analysis for Change from Baseline in CUA lesion count (see Section 14.3.1)
Tertiary (FAS by subgroup "High-relapse activity")	Period 6.2 (Month 6-12): #T2(p _{6.2})/#T2(p ₀)		
Tertiary (FAS by subgroup "Previous treatment with DMDs")	Period 6.3 (Month 12-18): #T2(p _{6.3})/#T2(p ₀) Period 6.4 (Month 18-24): #T2(p _{6.4})/#T2(p ₀)		
Tertiary endpoints: Change from the Baseline Period in Annualized Active T2 lesions count to the yearly post-Baseline Periods			
Tertiary (FAS)	Period 12.1 (Baseline-Month 12): ΔT2(p _{12.1})	Mixed-effects linear model for repeated measures as specified above.	Same as above for the mixed effect linear model with repeated measures.
Tertiary (FAS by subgroup "High-relapse activity")	Period 12.2 (Month 12-24): ΔT2(p _{12.2})		
Tertiary (FAS by subgroup "Previous treatment with DMDs")			
Tertiary endpoints: Ratio of the yearly post-Baseline Periods versus the Baseline Period in Annualized Active T2 lesions count			
Tertiary (FAS)	Period 12.1 (Baseline-Month 12): #T2(p _{12.1})/#T2(p ₀)	Generalized model as specified as above.	Same as above for the generalized model.
Tertiary (FAS by subgroup "High-relapse activity")	Period 12.2 (Month 12-24): #T2(p _{12.2})/#T2(p ₀)		
Tertiary (FAS by subgroup "Previous treatment with DMDs")			
Tertiary endpoint: Change from the Baseline Period in Annualized Active T2 lesions count to the 2-year post-Baseline Period			
Tertiary (FAS)	Period 24.1 (Baseline-Month 24): ΔT2(p _{24.1})	Mixed-effects linear model same as in Tertiary Analysis for Change from Baseline in CUA lesion count (see Section 14.3.1)	Same as in Tertiary Analysis for Change from Baseline in CUA lesion count (see Section 14.3.1)
Tertiary (FAS by subgroup "High-relapse activity")			
Tertiary (FAS by subgroup "Previous treatment with DMDs")			
Tertiary endpoints: Ratio of the 2-year post-Baseline Period versus the Baseline Period in Annualized Active T2 lesions count			
Tertiary (FAS)	Period 24.1 (Baseline-Month 24): #T2(p _{24.1})/#T2(p ₀)	Generalized model assuming a negative binomial, same as in Tertiary Analysis for Change from Baseline in CUA lesion count (see Section 14.3.1)	Same as above for the generalized model.
Tertiary (FAS by subgroup "High-relapse activity")			
Tertiary (FAS by subgroup "Previous treatment with DMDs")			

Analysis (Analysis Set)	Derivation	Statistical Analysis Methods	Missing data handling
Tertiary endpoint: Change from Baseline in Annualized active T2 Lesion count by Visit			
Tertiary (FAS)	Change from Baseline in active T2 Lesion count at Month i Visit, where i=1, 2, 3, 6, 12, 15, 18 and 24.	Mixed-effects linear model for repeated measures, same as in Tertiary Analysis for Change from Baseline in CUA lesion count (see Section 14.3.1)	Same as in Tertiary Analysis for Change from Baseline in CUA lesion count (see Section 14.3.1)
Tertiary (FAS by subgroup "High-relapse activity")			
Tertiary (FAS by subgroup "Previous treatment with DMDs")			
Tertiary endpoint: Active T2 Lesion count > 0			
Tertiary (FAS)	Cross-tabulation for each post-Baseline Visit 
 No: #T2(p_{post-Baseline})= 0 Yes: #T2(p_{post-Baseline})> 0 vs Baseline Period: 
 No: #T2(p₀) = 0 Yes: #T2(p₀)>0 	McNemar Test.	Same as for McNemar test in Section 14.3.1
Tertiary (FAS by subgroup "High-relapse activity")			
Tertiary (FAS by subgroup "Previous treatment with DMDs")			
Tertiary endpoint: Change from Baseline in Total T2 Lesion count by Visit			
Tertiary (FAS)	Change from Baseline in Total T2 Lesion count at Month i Visit, where i=1, 2, 3, 6, 12, 15, 18 and 24.	Descriptive summary statistics.	
Tertiary (FAS by subgroup "High-relapse activity")			
Tertiary (FAS by subgroup "Previous treatment with DMDs")			
$\Delta T2(p_i)$ = Difference in the standardized/annualized total active T2 lesion count between Period i and the Baseline Period Further Periods or comparisons may be added by an Amendment to the IAP (a) 6-month interim analysis			

14.3.8 Responder rate during the different Periods

Subjects will be classified as Responder for a post-Baseline Period if the standardized CUA lesion count decreased by at least 1 in 6 months in comparison to the Baseline Period:

- Responder: $\Delta\text{CUA}(p_i) = (\#\text{CUA}(p_i) - \#\text{CUA}(p_0)) * 6 \geq -1$, $i = \text{Period } 1, 2, 3$,
- Non-Responder: otherwise.

Subjects with missing assessments will be classified as “Non-Responder”.

Analysis (Analysis Set)	Derivation	Statistical Analysis Methods	Missing data handling
Tertiary endpoint: Responder rate during the different post-Baseline Periods ^(a)			
Tertiary (FAS)	Responder rates for Periods 1-3.	Descriptive summary statistics and 95% confidence intervals	Missing Baseline Period: Subjects with a missing CUA lesion count for the Baseline Period will not be included in analysis. Subjects with a missing post-Baseline Period will be classified as Non-Responder for the respective Period.
(a) 6-month interim analysis			

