4.3.1 Tertiary Endpoints

Safety:

- Occurrences of treatment-emergent adverse events (TEAEs) and serious adverse events (SAEs) including and up to 24 months

Clinical:

- Changes in Symbol Digit Modality Test (SDMT) outcome at the end of 6, 12, 18 and 24 months compared to baseline
- Disability evolution as measured by EDSS/KFS, 9-Hole Peg Test (9HPT), Timed 25-Foot Walk (T25FW) at the end of 6, 12, 18 and 24 months compared to baseline
- ARR between baseline and 24 months
- Changes in CUA lesions during the following post-baseline periods compared to baseline period (i.e. the period from screening to baseline):
 - Period of month 6 to month 12
 - Period of month 1 to month 12
 - Period of month 18 to month 24
 - Period of month 1 to month 24

Further periods and comparisons may be defined in the SAP

- Number of CUA lesions during the baseline and post-baseline periods
- Changes in active T1 Gd+ lesion count at the end of 1, 2, 3, 6, 12, 15, 18 and 24 months compared to baseline
- Volume changes of T1 Gd+ lesions at the end of 1, 2, 3, 6, 12, 15, 18 and 24 months compared to baseline
- Number of T1 hypointense lesions at the end of 1, 2, 3, 6, 12, 15, 18 and 24 months compared to baseline
- Change in volume of T1 hypointense lesions at the end of 1, 2, 3, 6, 12, 15, 18 and 24 months compared to baseline
- Changes in new T2 lesion count during the post-baseline periods compared to the baseline period as defined above
- Responder rate during the different periods as defined above with responder being defined as subjects with a CUA lesion count reduction of at least 1
- Changes in T2 lesion volume at the end of 12 and 24 months compared to baseline
- Changes in Magnetization Transfer Ratio (MTR) at the end of 1, 2, 3, 6, 12, 15, 18 and 24 months compared to baseline
- Changes in brain volume at the end of 1, 2, 3, 6, 12 and 24 months compared to baseline (and changes at 24 months compared to 6 months to exclude pseudo-atrophy)
- No Evidence of Disease Activity (NEDA) at 24 months
- No Evidence of Progression or Active Disease (NEPAD) at 24 months

CCI [REDACTED]

[figure not shown]

5 Investigational Plan

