6.1 Interim Analysis

An interim analysis for primary endpoint that includes all planned sensitivity analyses will be undertaken after all subjects have completed the 6-month assessment.

In addition, the Interim Analysis will describe the following characteristics of the study population up to the cut-off:

- Disposition of Participants and Discontinuations (Section 10.1),
- Major Protocol Deviations (Section 10.2),
- Demographics and Other Baseline Characteristics (Section 11):
 - Baseline Characteristics (Section 11.2),
 - Medical History (Section 11.1),
 - MS Disease Characteristics (Section 11.2),
 - Vital Signs (Section 11.2).
- Previous or Concomitant Medications/Procedures (Section 12),
- Treatment Compliance and Exposure (Section 13),

and will evaluate the following tertiary and safety endpoints up to 6 months Visit or the cut-off point:

- Number of CUA lesions during the Baseline and post-Baseline Periods (Section 14.3.2),

- T1 Gd+ lesion count by Visit and mean T1 Gd+ lesion count during the Baseline and post-Baseline Periods (Section 14.3.3),
- Changes in Standardized total active T2 lesion count during the post-Baseline Periods compared to the Baseline Period (Section 14.3.7),
- Responder rate during the different Periods (Section 14.3.8),
- Relapse reports including and up to the cut-off point (Number and Percentage of Subjects with (qualifying) relapses),
- Adverse Events (Section 15.1),
- Clinical Laboratory Evaluation (Section 15.3),
- Vital signs (Section 15.4).

The characteristics of the population as well as relapses will be summarized descriptively up to Month 6 Visit in the same way as for the final analysis. The tertiary MRI endpoints and Safety endpoints will be analyzed up to the Month 6 Visit or cut-off date in the same way as for the final analysis, as applicable.

Table 1 lists all assessments which will be included in the interim analysis.

Table 1: List of assessments included in the interim analysis

Assessments	Screenin g	Baselin e	Month 1	Month 2	Month 3	Month 6
Informed Consent	X					
Demographics	X					
Weight		X	X			
Vital Signs	(X)	X				
Medical History	X					
Disease History	X					
Relapse History		X				
MRI	X	X	X	X	X	X
Disability (EDSS/KFS)	X	X				
Relapse count			X	X	X	X
Lymphocyte Count	X			X		X
Treatment Administration		X	X			
AEs		X	X	X	X	X
Concomitant medications and procedures	X	X	X	X	X	X
Relevant previous medications	X					

Assessments	Screening	Baseline	Month 1	Month 2	Month 3	Month 6

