The primary analysis and selected demographic and background characteristics as well as selected tertiary analyses will be repeated for these subgroups.

The following subset(s) are defined:

- Baseline Period CUA count > 0 (i.e. all subjects with a CUA lesion count > 0 during the Baseline Period)

As subjects with a CUA count of 0 during the Baseline Period cannot show an improvement in the number of CUA lesions during the study, some of the efficacy analyses will be repeated for this subset that has at least one CUA lesion during the Baseline Period.

9 General Specifications for Data Analyses

Treatment groups

The treatment group will be labeled as Mavenclad®.

Significance level

The three hypotheses of the primary analysis (see Section 14.1) will be tested as one -sided, on a 2.5% significance level. The testing procedure will stop as soon as one of the hypotheses cannot be rejected following a pre-specified order. Due to this sequential order of tests an adjustment for a potential type-I-error inflation due to the multiple testing is not required.

CCI [REDACTED] All statistical tests will be performed two-sided. If confidence intervals are to be calculated, these will be two-sided with a confidence probability of 95%, unless otherwise specified in this IAP.

Presentation of continuous and qualitative variables

Continuous variables will be summarized using descriptive statistics, i.e., number of subjects, number of subjects with missing and non-missing values, mean with standard deviation, median, 25th Percentile - 75th Percentile (Q1-Q3), minimum, and maximum.

Qualitative variables will be summarized by counts and percentages.

Unless otherwise stated, the calculation of proportions will be based on the number of subjects in the analysis set of interest. Therefore, counts of missing observations will be included in the denominator and presented as a separate category.

In case where the analysis refers only to certain Visits, percentages will be based on the number of subjects still present in the study at that Visit, unless otherwise specified.

Definition of Baseline

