- Period 100.1 (p_{100.1}) is defined as the Period between Baseline and Month 1 MRI scans,

- Period 100.2 (p_{100.2}) is defined as the Period between Month 1 and Month 2 MRI scans,
- Period 100.3 (p_{100.3}) is defined as the Period between Month 2 and Month 3 MRI scans,
- Period 100.6 (p_{100.6}) is defined as the Period between Month 3 and Month 6 MRI scans,
- Period 100.12 (p_{100.12}) is defined as the Period between Month 6 and Month 12 MRI scans,
- Period 100.15 (p_{100.15}) is defined as the Period between Month 12 and Month 15 MRI scans,
- Period 100.18 (p_{100.18}) is defined as the Period between Month 15 and Month 18 MRI scans,
- Period 100.24 (p_{100.24}) is defined as the Period between Month 18 and Month 24 MRI scans.

Note: Period start and end dates are defined by the MRI dates as provided by central reading.

Definition of change from Baseline

Change from Baseline = Visit value – Baseline value.

Percentage Change from Baseline = $100 \times (\text{Visit value} - \text{Baseline value}) / \text{Baseline value}$.

The Percentage Change from Baseline will be set to missing for subjects with a zero at Baseline.

Definition of Visit dates

The Visit start date is the date of the first assessment which belongs to the corresponding Visit.

The Visit end date is the date of the last assessment which belongs to the corresponding Visit.

Definition of duration

Duration will be calculated by the difference of start and stop date + 1, in days (unless specified otherwise).

Treatment Period

The treatment Period begins with the start of study medication on Study Day 1 and continues through to the completion of the treatment Period at the Month 24 Visit (see CSP, Section 7.1.2). Start of study medication is the date of first intake of study medication. Start of study medication in Year 2 is the date of first intake of study medication at or after the Month 12 Visit.

Treatment Period:

- Start = Start of study medication,
- End = Visit end date of Month 24 Visit, or Early Termination (ET) Visit, in case of early discontinuation, or the study discontinuation date, if the ET Visit was not performed.

Course 1 Treatment Period:

- Start = Start of study medication,

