14.1.1 Primary Objective: Analysis of primary endpoints

The differences in counts of CUA lesions will be evaluated using a mixed-effects linear model, accounting for within-center/region correlation through a hierarchical model. The analysis will adjust for Baseline factors deemed to be prognostic for the primary endpoint, as judged by clinical experts:

- CUA lesion count during the Baseline Period,
- Age,
- EDSS at Baseline ($\leq 3 / > 3$).

The results of the mixed-effects linear model will be used to describe the effect size. A review of Baseline data has shown that the distribution of the primary endpoint data does not follow Normal distribution. Consequently, the hypotheses will be tested by a Wilcoxon signed-rank test which employs ranks of absolute differences from Baseline for each testing Period (i.e., p_1 , p_2 , and p_3) using average ranks for tied values.

The analysis will also adjust for the difference in length and number of MRIs of the Periods to be compared (see Section 9 “Data Handling of MRI data” for details of lesion count standardization).

The difference in the counts of CUA lesions during the three Periods compared to the Baseline Period will be tested in a sequential order. The three hypotheses are defined as follows:

$$H_{0i}: \Delta \text{CUA}(p_i) \geq 0 \quad \text{vs.} \quad \Delta \text{CUA}(p_i) < 0, \quad i = 1, 2, 3$$
$$\Leftrightarrow H_{0i}: \#\text{CUA}(p_i) \geq \#\text{CUA}(p_0) \text{ vs. } \#\text{CUA}(p_i) < \#\text{CUA}(p_0), \quad i = 1, 2, 3$$

with

$$\Delta \text{CUA}(p_i) = \#\text{CUA}(p_i) - \#\text{CUA}(p_0), \quad i = 1, 2, 3,$$

$$\#\text{CUA}(p_i): \text{standardized CUA lesion count during Period } p_i, \quad i = 0, 1, 2, 3,$$

p_0 : Baseline Period (Period from Screening to Baseline),

p_i : Period Month i to Month 6, $i = 1, 2, 3$.

The sequential testing procedure will start with Period p_3 , followed by Period p_2 and p_1 , i.e., the hypotheses will be tested in the following order:

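### SAP 14.3.8 prints the responder inequality reversed (≥ −1 where its own text needs ≤ −1); read as printed, unchanged, worsening and zero-Baseline subjects are Responders

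*SAP*

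**What the plan says.** SAP 14.3.8 gives the responder rule twice. In words: "Subjects will be classified as Responder for a post-Baseline Period if the standardized CUA lesion count decreased by at least 1 in 6 months", relative to the Baseline Period. The formula that follows, for Periods 1, 2 and 3, ends "CUA}(p_i) - \#\text{CUA}(p_0)) * 6 \geq -1" (the typesetting code means ≥ −1), and the complement is "Non-Responder: otherwise".

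Other places fix the direction:

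- SAP Section 9, on change from Baseline: "Change from Baseline = Visit value – Baseline value". SAP 14.1.1 defines ΔCUA in the same way, as the Period count minus the Baseline Period count, with improvement as the alternative ΔCUA < 0.
- Protocol 4.3.1 (also the Synopsis and 8.3.3): "responder being defined as subjects with a CUA lesion count reduction of at least 1".
- SAP Section 7 says that the definition refers to the standardized count. It does not change the direction.
- SAP 8.2: "subjects with a CUA count of 0 during the Baseline Period cannot show an improvement in the number of CUA lesions during the study".

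SAP 6.1 lists this rate among the endpoints of the 6-month analysis, and the 14.3.8 table reports it with 95% confidence intervals.

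**The concern.** The sentence and the formula cannot both be followed. With post minus Baseline, a fall of at least 1 in 6 months means a scaled difference of −1 or lower. The printed inequality selects the other side of the cut-off. It admits every evaluable subject with no change, with an increase, or with no Baseline lesions, although SAP 8.2 says the last group cannot show improvement. It also rejects subjects whose lesions clear completely, unless they started at or below 1/6 on the standardized scale.

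If the formula was programmed literally, a protocol-listed endpoint would be reported close to its complement, and the rate would fall as lesion suppression improved. No other place in the SAP prints the rule with the correct sign.

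**Working it through.** **Direction of the inequality.** Let D = 6 × (#CUA(p_i) − #CUA(p_0)). A decrease of at least 1 in 6 months is D ≤ −1. If the difference were taken the other way (Baseline minus post), the condition would be ≥ +1. Neither convention gives ≥ −1. SAP 14.3.11 handles the same construction correctly: a brain volume loss of at least 0.4% is coded as an annualized change ≤ −0.4%.

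**Worked subjects.** From SAP Section 9 (data handling of the primary MRI endpoint):

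#CUA = mean Gd+ count per scan + (active T2 lesions without Gd+) × 30.4375 / period length, with period length = days between scans + 1.

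Assumed spacing: Screening and Baseline scans 60 days apart (length 61), Month 3 and Month 6 scans 91 days apart (length 92). Period 3 is used, with two scans in each period.

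| Baseline Period → Period 3 | #CUA(p_0) | #CUA(p_3) | D | By the words | As printed |
|---|---|---|---|---|---|
| Gd+ 2,2 → 0,0 | 2 | 0 | −12.0 | Responder | Non-Responder |
| Gd+ 1,1 plus one T2 → none | 1 + 30.4375/61 = 1.499 | 0 | −8.99 | Responder | Non-Responder |
| none → none | 0 | 0 | 0 | Non-Responder | Responder |
| none → one Gd+ at Month 6 | 0 | 0.5 | +3.0 | Non-Responder | Responder |
| Gd+ 1,1 → 2,2 plus three T2 | 1 | 2 + 3 × 30.4375/92 = 2.993 | +11.96 | Non-Responder | Responder |

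The two rules agree only at exactly D = −1, for example in Period 2 with 0.5 → 0.333: 6 × (−1/6) = −1. Missing data are unaffected: in the 14.3.8 table a missing post-Baseline Period is a Non-Responder and a missing Baseline Period is excluded, whatever the inequality.

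**Effect on the rate.** Among evaluable subjects, ignoring ties at −1:

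printed responders = evaluable subjects − correct responders.

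For the planned 265 subjects (Protocol Synopsis), with assumed correct rates:

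- 212 correct (80%): 265 − 212 = 53 printed (20%)
- 159 correct (60%): 265 − 159 = 106 printed (40%)
- 80 correct (30%): 265 − 80 = 185 printed (70%)
- 159 correct (60%) with 13 post-Baseline Periods missing (assumed): 252 evaluable − 159 = 93 printed, and 93/265 = 35%

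**Direction with efficacy.** The documents give no lesion distribution. An illustration with assumed gamma-Poisson counts and Baseline means of 0.5, 1 and 2 gives:

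| | Printed rule | Worded rule |
|---|---|---|
| No treatment effect | 75%, 69%, 65% | 25%, 31%, 35% |
| Complete suppression | 54%, 39%, 26% | 46%, 61%, 74% |

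Under complete suppression the printed rate is simply the share of subjects with a zero Baseline count.

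**The case against.** The strongest reply is that the intended rule is easy to recover. The sentence directly above the formula, the Protocol definition and SAP 8.2 all give the direction, and a programmer who read the sentence or looked at the output would probably have noticed. What the documents establish is an inconsistent line in the SAP, not a misclassified result. That stands, and the conclusion is conditional for that reason. It does not remove the need to check: the formula is the operational specification, and the SAP modification history (version 3.0) records that a sensitivity analysis was implemented differently from what the plan specified.

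A second reply is that the point rests on one symbol read from a PDF. A misread cannot be fully excluded, so the source file should be looked at first.

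Third, the effect is narrow: a tertiary, descriptive rate for three Periods at the 6-month analysis, with no hypothesis test attached. SAP Section 7 refers to decisions made after the primary analysis had been performed, so a correction now mainly serves to verify existing output. This is right, and it limits the weight of the point.

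Finally, the factor 6 means that a standardized reduction of only 1/6 qualifies, whereas the Protocol speaks of a reduction of at least 1 and SAP Section 7 does not mention the factor. Also, the Gd+ part of #CUA is a per-scan mean rather than a strict monthly count. Both observations are fair. But the factor implements the SAP's own 6-month wording, and neither affects the direction of the inequality.

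**Conclusion.** The concern holds. The printed inequality in SAP 14.3.8 contradicts the sentence above it, the SAP's sign convention, the Protocol definition and the statement in SAP 8.2 about zero-Baseline subjects. Followed literally, it replaces the responder count among evaluable subjects by its complement, apart from ties at exactly −1. That relation is algebra. The 30%, 60% and 80% rates, the 13 missing Periods, the scan spacing and the simulated distribution are assumptions used to show scale, and none of them estimates an actual error in reported results. The primary Wilcoxon sequence is not touched. Whether any output is wrong depends on the sign in the program, which the documents do not show. This should be fixed, because the correction is trivial and the possible consequence is a reversed result on a listed endpoint.

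**What to change.** 1. Confirm the symbol in the SAP source file.
2. Correct 14.3.8 to: Responder if 6 × (#CUA(p_i) − #CUA(p_0)) ≤ −1; Non-Responder if the value is > −1 or the post-Baseline Period is missing. Keep the factor 6.
3. Check the program behind the 6-month responder table, and re-issue the table only if it used ≥ −1.
4. As a minor tidy-up, limit the sentence in 14.3.8 that makes subjects with missing assessments Non-Responders to missing post-Baseline Periods, since the table in the same section already excludes subjects with a missing Baseline Period.

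The cost is a one-character erratum and a check of one program, plus one table re-run if the printed sign was used.
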